Official Title: Aspirin as Adjuvant Therapy in Young Psychotic Patients NCT number: NCT02685748

Study Protocol and Statistical Analysis Plan

Effect of adjuvant aspirin therapy on neurological soft signs and PANSS in young psychotic patients

A randomized, interventional, double-blind, placebo-controlled clinical trial

Protocol name:	Aspirin2016.2
Date:	25 October 2016.
Donor:	Stanley Medical Research Institute, [name], [name] 20815, SAD
Sponsor:	Clinic for Mental Diseases "[name]", [name], Serbia
Principal Investigator, Grant Holder:	MD [name], psychiatrist
Co-investigators:	MD/PhD [name], neuropsychiatrist MD [name], psychiatrist MD [name], psychiatrist

Background:

The clinical trial team would conduct a randomized, interventional, double-blind, placebo-controlled study in two parallel groups of patients who were neuroleptically naive or previously minimally medicated (who did not take antipsychotics during the previous 6 months) with the illness duration of up to seven years. Patients of both sexes, ages 18 to 28, would participate in the trial, in accordance with the tenth revision of the International Classification of Diseases (ICD10), they would meet the diagnostic criteria for the illnesses ranging from F 20 to F 29. After meeting the inclusion and exclusion criteria and having signed an informed consent form, the patients would be randomized into two groups:

Experimental group - EG: antipsychotic + Aspirin

and

Control group – CG: antipsychotic + placebo.

The EG patients would be administered 1000 mg aspirin pro die with gastric protection pantoprazole 40 mg pro die, both medicines in two doses during 6 weeks of hospital treatment at Clinic form Mental Disorders "[name]". The trial would last for 18 months and would include the total of 100 to 120 patients.

Objective and hypotheses:

The objective of the trial would be to determine the effect of adjuvant aspirin therapy on neurological soft signs, positive and negative syndrome in schizophrenia, cognition, inflammatory factors and cytokine profile.

Working hypotheses:

- 1. Changes in PANSS and MoCA scores as well as inflammation factors in both patient groups, more in the experimental group.
- 2. Changes in the cytokine profile in both patient groups.
- 3. In case of significant change of SNS and cytokine profile in the experimental group the results would support the cytokine hypothesis. If there were no significant changes in the SNS in the experimental group, the results would support the SNS as a trait of schizophrenia.

Clinical Trial Design:

A randomized, interventional, double-blind, placebo-controlled clinical trial in two parallel groups of patients who were neuroleptically naive or previously minimally medicated (who did not take antipsychotics during the previous 6 months) with the illness duration of up to seven years. Patients of both sexes, ages 18 to 28, would participate in the trial, in accordance with the tenth revision of the International Classification of Diseases, would meet the diagnostic criteria for the illnesses ranging from F20 to F29. Upon fulfilment of inclusion and exclusion criteria and signed Informed consent form, they would be randomized in two groups: experimental (EG) and control group (CG). Patients belonging to the control group would be administered antipsychotic therapy and placebo, whereas patients in the experimental group would be administered regular antipsychotic therapy and aspirin. EG patients would be administered 1000 mg aspirin pro die with gastric protection- pantoprazole 40 mg pro die, both medicines in two doses in duration of 6 weeks.

A software application specialized in the randomization of subjects for clinical trials -*Sealed Envelope* - will be used for randomization. The obtained list will be in possession of one co-investigator and only he or she will know which group the patient belongs to. Only upon completion of the trial, after taking the serum samples from the last patient, and cytokine profile analysis (cytokine profile analysis would be performed at the end of the trial, after the serum sample from the last patient was taken at both test times) would the patient's belonging to the EG or CG group be revealed.

The co-investigator in charge of randomization would give out the medicine boxes and the medicines would all look identical - packed in the same capsules for overcapsulation by the company **Capsugel**. Placebo tablets would be manufactured by Galenika A.D. The patient would be administered Bayer's Aspirin tbl. á 500 mg and Nolpaza tbl. á 20 mg produced by Krka-Farma D.O.O.

Three visits are planned. The first visit after admission to the Clinic. If the patient fulfils the inclusion criteria and none of the exclusion criteria (anamnestic data, somatic and psychiatric examination), and after the Informed consent form has been signed, PANSS scale test and blood sample would be taken for laboratory analysis. Laboratory analysis would be complete blood count (RBC, WBC, PTC, Hgb, Hct), sedimentation, C reactive protein, blood biochemical analysis (glycaemia, cholesterol, triglycerides, transaminases, CK, bilirubin, uric acid, creatinine, urea), and electrolytes (Na, K). Th1, Th2 and Th17 cytokines would be subject to the immunological assays. Each patient would be given an identification number (from one upwards) and the tubes with serum for the cytokine profile would be labelled with the same number, in terms of x/y, where x is the patient's identification number and y- may be "1" or "2" ("a" or "b"), where "1" or "a" would mean the first blood draw (at the beginning of the trial) and the number "2" or "b" - the second blood draw (at the very end of the trial).

After calming down of the acute signs of psychosis, between the third and fifth day of hospitalization, the second visit would be made when testing of the neurological soft signs would be performed according the Heidelberg Soft Neurological Signs Scale, the MoCA Cognitive Assessment Scale, and then the patient would be randomized to an experimental or control group if he/she meets the inclusion and no-exclusion criteria, if there are no somatic contraindications (with a stable ECG), and if he/she still wishes to participate in the trial.

The staff of the ward where the patient would be accommodated would be given two boxes of medicines labelled "Clinical Trial Medication 1" and "Clinical Trial Medication 2" that would be administered to patients – one medicine from each box, in the morning and in the evening.

After 6 weeks from the second visit (+/- 3 days), the third visit would be made when the patient would be examined, the PANSS, MoCA and Heidelberg scales testing repeated, and the blood sample taken again for laboratory analyses - inflammatory factors and cytokine profiles.

Control laboratory analyses would be performed on each patient on days 14th and 28th from the second visit. If patients received high dose valproic acid in therapy, valproatemia control would be performed, and if they received antidepressants from the SSRI group, bleeding time would be controlled.

Serums administered to patients would be transported in a cold chain to the Centre for Molecular Medicine and Stem Cell Research at the Faculty of Medical Sciences, University of Kragujevac, where they would be stored at -70°C until analyses were performed.

Criteria for Trial Termination:

The criteria for trial termination for individual subjects, parts of the trial or the whole trial would be defined as follows: the subject may voluntarily leave the trial at any moment. In the event that side effects of adjuvant aspirin therapy occur, the patient would be excluded from the trial. Occurrence of bleeding from the nose or gums, bruising, bleeding in the GIT or brain, and confusion, anaphylactic reactions or acute renal failure would imply the immediate exclusion of subjects from the trial. If there is an increase in valproatemia (in patients taking valproic acid in therapy) - the dose of the medicine would be excluded from the trial. The entire trial would be discontinued by the emergence of a large number of complicated side effects, as well as by compromising drug storage.

Selection and inclusion of subjects:

Inclusion criteria:

- Age 18 to 28
- Diagnostic categories from F 20 to F 29
- Illness duration \leq 7 years

> Exclusion criteria:

- PAS abuse
- Primary cognitive impairment
- Contraindications and special caution for acetylsalicylic acid and pantoprazole:
 - Hypersensitivity to acetylsalicylic acid and other NSAIDs (possible cross-reaction)
 - Gastric ulcer and/or duodenum ulcer, gastritis
 - Pregnancy
 - Haemophilia, bleeding disorders
 - Gout

- Asthma, COPD, NSAID-induced bronchospasm
- Angioedema, urticaria
- Haemolytic anaemia
- Use of warfarin, methotrexate
- Diabetes
- Decreased liver and / or kidney function
- Heart failure
- Surgical/dental intervention
- Interactions with specific psycho-pharmaceuticals
- Sensitivity to pantoprazole

Statistical analysis plan:

Statistical data analysis will be done in the programme IBM SPSS Statistics v.20.

Continuous variables will be displayed descriptively using the minimum and maximum values, mean values and standard deviation. Categorical variables will be presented descriptively using absolute and relative frequency as well as graphically using a pie chart.

Kolmogorov-Smirnov or Shapiro-Wilk test, depending on sample size, will be used to check the normality of data distribution, as well as graphical method of using histogram. If the data follow the normal distribution, parametric tests will be used for the statistical analysis of the data; otherwise the corresponding non-parametric tests will be used.

For the analysis of significant continuous variables over time, the Paired Samples t Test will be used if the data follow a normal distribution or the Wilcoxon test if the data do not follow the normal distribution. Significant results will be presented graphically using a bar chart or boxplot.

For the analysis of significant difference of continuous variables between the control and experimental groups, the Independent Samples t Test will be used if the data follow a normal distribution or the Mann-Whitney test if the data do not follow the normal distribution. Significant results will be presented graphically using a bar chart or boxplot.

For the analysis of the dependence between two continuous variables, the value of Pearson's or Spirman's correlation coefficient will be interpreted. In the case of strong correlations, the dependence will be shown both by the regression equation and graphically using the scatterplot.

For the analysis of the dependence between the two categorical variables, a Chi-squared test, that is, a Fisher's exact-dependency test will be used. The results will be presented graphically using a bar cluster graph.

The results will be considered statistically significant if the p value is less than 0.05.

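### Hypothesis 2 predicts cytokine change in both arms with no aspirin-versus-placebo contrast, so meeting it would not show the aspirin effect that the objective asks about

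*Combined protocol and SAP*

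**What the plan says.** **Objective.** Under Objective and hypotheses, the trial is to "determine the effect of adjuvant aspirin therapy on neurological soft signs, positive and negative syndrome in schizophrenia, cognition, inflammatory factors and cytokine profile". In a randomised placebo-controlled trial that is a comparison of EG with CG.

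**Working hypotheses.**
- Hypothesis 1: "Changes in PANSS and MoCA scores as well as inflammation factors in both patient groups, more in the experimental group". It contains a between-arm clause, but does not name cytokines.
- Hypothesis 2, complete: "Changes in the cytokine profile in both patient groups". It gives no contrast, direction or size.
- Hypothesis 3: "In case of significant change of SNS and cytokine profile in the experimental group the results would support the cytokine hypothesis". Cytokines appear jointly with neurological soft signs, and only as change within EG.

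**Are cytokines among the inflammation factors of hypothesis 1?** The objective ends "cognition, inflammatory factors and cytokine profile", and the third-visit text under Clinical Trial Design has "inflammatory factors and cytokine profiles". Both list them as separate items.

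**Tests.** The Statistical analysis plan section offers a paired t or Wilcoxon test for change over time, and an independent-samples t or Mann-Whitney test for EG against CG. Both are generic to continuous variables. Neither is assigned to a hypothesis, and the between-arm test is not said to be on change from baseline.

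**The concern.** Both arms receive an antipsychotic; the control arm is "antipsychotic + placebo". The design describes patients as untreated or as people "who did not take antipsychotics during the previous 6 months". The first blood sample is taken at the first visit after admission, before the acute signs have settled, and the last about six weeks after the second visit. Start of treatment and recovery from the episode are therefore common to both arms, and cytokine levels may move in both whatever aspirin does. Hypothesis 1 itself expects change in both groups on other measures.

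A prediction of change in both arms does not separate aspirin from these shared influences. The SAP test that matches its wording is the paired one, applied arm by arm. A report could then present hypothesis 2 as supported when CG changed as much as EG, and hypothesis 3 could carry a within-EG change forward as support for the cytokine hypothesis.

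**Working it through.** **The plan's own figure.** The total is 100 to 120 patients. No effect size, SD, power or drop-out is given, so it cannot be reproduced.

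**Inputs from the documents.** Total 100 to 120; two groups; significance at p < 0.05; paired and independent-samples tests.

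**Assumptions, because the documents are silent.** 1:1 allocation, so n = 50 or 60 per arm; two-sided tests; no drop-out; one cytokine (the panel is Th1, Th2 and Th17, number of analytes not given); normally distributed changes with equal SD. Standardised change d = mean change ÷ SD of individual changes, taken over a range.

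**Reading of hypothesis 2.** Met if the paired test is significant in EG and in CG. This is an inference from the wording.

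**Formulas.**
- Paired power in one arm, p(d): noncentral t with n − 1 df and noncentrality d√n.
- The arms are independent, so P(hypothesis 2 met) = p(d in EG) × p(d in CG).
- Between-arm test of change: noncentral t with 2n − 2 df and noncentrality (d in EG − d in CG) × √(n/2).

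At d = 0.5 and n = 50, the paired noncentrality is 0.5 × √50 = 3.54, giving p = 0.934; for the between-arm test with CG at zero it is 0.5 × √25 = 2.5, giving power 0.697.

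**Case A: aspirin inert, same change in both arms.**

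| Shared d | n = 50 | n = 60 |
|---|---|---|
| 0 | 0.05² = 0.25% | 0.25% |
| 0.3 | 0.548² = 30% | 0.628² = 39% |
| 0.5 | 0.934² = 87% | 0.968² = 94% |

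A between-arm test of change rejects in 5% of trials in every row.

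**Case B: EG changes, CG flat.**

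| d in EG | Hypothesis 2 met, n = 50 / 60 | Between-arm power, n = 50 / 60 |
|---|---|---|
| 0.3 | 0.548 × 0.05 = 2.7% / 0.628 × 0.05 = 3.1% | 32% / 37% |
| 0.5 | 0.934 × 0.05 = 4.7% / 0.968 × 0.05 = 4.8% | 70% / 78% |
| 0.6 | 0.986 × 0.05 = 4.9% / 0.995 × 0.05 = 5.0% | 84% / 90% |

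The first result cannot exceed 5%, because the CG factor is 0.05 and the EG factor is at most 1.

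**Case C: both arms change and aspirin adds to it** (CG 0.5, EG 1.0). Hypothesis 2 is met in 93% (n = 50) to 97% (n = 60). With inert aspirin and the same CG change it was met in 87% to 94%, so the criterion hardly tells the two situations apart. The between-arm test moves from 5% to 70–78%.

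**Check.** Simulation with 20,000 trials per setting gave 87.2% and 93.8% for Case A at 0.5, and 69.9% and 77.3% between-arm power for Case B at 0.5.

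**The case against.** Four points can fairly be made for the plan.

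1. **The success rule is inferred.** These are called working hypotheses, and nothing says when one is confirmed or rejected. Hypothesis 2 may be only a background expectation under antipsychotic treatment. This stands, and the percentages depend on the reading. But on the background reading no hypothesis states an aspirin effect on cytokines at all.

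2. **A between-arm test exists.** The SAP's independent-samples test covers continuous variables and so could be run on cytokines. This also stands: the trial is not without means to answer the question. What is missing is any link from that test to this hypothesis, and any statement that it is on change.

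3. **The two adverse cases rest on opposite premises.** Case A needs a shared change; Case B needs a flat control arm, which the argument for shared change makes less likely. This is correct. A reader might infer that hypothesis 2 will be confirmed whenever aspirin does nothing and rejected whenever it works. The documents support neither: the first happens in 0.25% of trials without a shared change, and in Case C, where aspirin works, hypothesis 2 is usually met. Case C, however, needs no opposed premise and shows the same weakness.

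4. **Cytokines are not the headline outcome.** The trial title names soft signs and PANSS, and no text makes cytokines primary. That limits the severity. Cytokines remain a named objective and one leg of hypothesis 3.

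**Conclusion.** The point holds in conditional form. As worded, hypothesis 2 states no EG-versus-CG contrast; hypothesis 1's contrast does not clearly reach cytokines; hypothesis 3 uses EG alone. So no hypothesis clearly states the between-arm cytokine effect that the objective asks for.

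Under the both-arms-significant reading, the chance of meeting hypothesis 2 with inert aspirin runs from negligible to above 90%, depending on the size of the shared change; with a flat control arm it is capped at 5% whatever aspirin does. These figures rest on the assumed effect sizes, allocation, complete data and single analyte listed above. The direction does not: paired change in both arms does not isolate aspirin at any effect size.

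It would go too far to say that the trial has no way to test aspirin's effect on cytokines, or that conduct, sample size or safety is affected. The defect lies in the hypothesis and in what may be concluded from it. Severity: should-fix.

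**What to change.** - Restate hypothesis 2 as: *The change in cytokine levels from baseline to week 6 differs between EG and CG.*
- Say in the SAP that this hypothesis is tested between arms, either on change from baseline or on the week-6 value adjusted for baseline. The existing independent-samples test serves for the first, once it is said to be on change.
- Keep the within-arm paired tests for cytokines as description only.
- Base the cytokine part of hypothesis 3 on the same between-arm contrast.
- Name the cytokines to which the hypothesis applies, since the proposed sentence alone does not.

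The cost is a few sentences in the hypotheses and the SAP, with no new data, visits or patients. Under Clinical Trial Design, allocation is revealed only after the cytokine assays, so the wording can be settled while allocation is still concealed. With 50 to 60 per arm, the between-arm test would detect a difference in change of about 0.56 to 0.51 SD with 80% power, from (1.96 + 0.84) × √(2/n). Smaller effects may be missed, and the report should allow for that.

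### Hypothesis 3 judges the cytokine hypothesis on change within the aspirin arm alone, so if soft signs also change without aspirin its error rate is not set by the 0.05 threshold

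*Combined protocol and SAP*

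**What the plan says.** All places are in the combined protocol and SAP.

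- **Objective and hypotheses, objective:** "The objective of the trial would be to determine the effect of adjuvant aspirin therapy on neurological soft signs", with cytokine profile among the further outcomes.
- **Working hypothesis 1:** "Changes in PANSS and MoCA scores as well as inflammation factors in both patient groups, more in the experimental group". This compares the groups, but lists neither SNS nor cytokines.
- **Working hypothesis 2:** "Changes in the cytokine profile in both patient groups".
- **Working hypothesis 3, first sentence:** "In case of significant change of SNS and cytokine profile in the experimental group the results would support the cytokine hypothesis". The control group (CG) is not mentioned.
- **Working hypothesis 3, second sentence:** "If there were no significant changes in the SNS in the experimental group, the results would support the SNS as a trait of schizophrenia". SNS change is therefore treated as an open question.
- **Clinical Trial Design, treatment:** "Patients belonging to the control group would be administered antipsychotic therapy and placebo". The experimental group (EG) also receives antipsychotics.
- **Clinical Trial Design, visits:** at visit 1, "PANSS scale test and blood sample would be taken for laboratory analysis". That draw is the first cytokine sample. SNS is first tested at visit 2, on hospital day 3 to 5 once acute signs have settled, and randomisation follows. Both are measured again at visit 3, six weeks later.
- **Statistical analysis plan:** paired t or Wilcoxon tests for change over time; independent-samples t or Mann-Whitney tests between the groups; significance at p below 0.05. No test is assigned to any hypothesis. The plan does not say whether the between-group test applies to change or to visit 3 values.

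**The concern.** Change within EG is the sum of any aspirin effect and everything the arms share: antipsychotic treatment after at least six months without it, six weeks in hospital, and retesting. Only the comparison with CG separates the two. The first sentence of hypothesis 3 does not call for that comparison, and the paired test fits its wording most directly.

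The cytokine half of the rule gives little protection, because hypothesis 2 expects cytokines to change in CG as well. The measured cytokine change in EG also begins before any aspirin is given. The SNS half protects only if SNS is stable without aspirin, which the documents neither state nor deny.

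At stake is a named conclusion of a randomised, placebo-controlled trial. It could be declared when aspirin has no effect, with a probability that depends on the size of the shared change and not on 0.05.

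**Working it through.** **Inputs from the documents.** Total sample 100 to 120; threshold 0.05; paired t test for change over time; the rule needs both SNS and cytokine change.

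**Assumptions, not in the documents.** 1:1 allocation (100/2 = 50 and 120/2 = 60 in EG), no dropout, two-sided tests, one cytokine measure, normally distributed change scores, and no aspirin effect. The null is taken as no aspirin effect because that is the stated objective; the documents do not define the cytokine hypothesis. The shared change d is in units of the SD of change. The documents give no value for it, so a range is shown. Paired figures are for n = 50 / n = 60.

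**Step 1. One outcome, paired t test in EG.** The test statistic is noncentral t with n − 1 degrees of freedom and noncentrality d√n, so

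p(d) = P(|t′(n − 1, d√n)| > t(0.975, n − 1)).

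At d = 0 this returns the plan's own 0.05. At d = 0.2 the noncentrality is 0.2 × √50 = 1.41 or 0.2 × √60 = 1.55, and p = 0.284 / 0.332.

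**Step 2. Both outcomes, same d.** If they are independent, the rule is met with probability p². The correlated cases are simulated.

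| Shared change d | One outcome, p | Joint, independent (p²) | Joint, correlation 0.5 | Joint, correlation −0.5 |
|---|---|---|---|---|
| 0 | 0.050 / 0.050 | 0.0025 / 0.0025 | 0.009 / 0.009 | 0.009 / 0.009 |
| 0.1 | 0.107 / 0.119 | 0.011 / 0.014 | 0.033 / 0.039 | – |
| 0.2 | 0.284 / 0.332 | 0.080 / 0.110 | 0.143 / 0.180 | 0.031 / 0.050 |
| 0.3 | 0.548 / 0.628 | 0.300 / 0.394 | 0.380 / 0.469 | 0.223 / 0.326 |
| 0.5 | 0.934 / 0.968 | 0.872 / 0.937 | 0.885 / 0.942 | – |

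The joint rate passes 5% at d = 0.173 / 0.157 (independent), 0.125 / 0.113 (correlation 0.5) or 0.220 / 0.200 (correlation −0.5). Below those values the rule is conservative.

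**Step 3. Dropout of 20%** (50 × 0.8 = 40 and 60 × 0.8 = 48 in EG), independent outcomes: 0.055 / 0.075 at d = 0.2 and 0.208 / 0.281 at d = 0.3.

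**Step 4. SNS stable, cytokine changing.** The joint probability cannot exceed that of the SNS test alone, so it is at most 0.05 whatever the cytokine does. For n = 50 and independent outcomes it is 0.05 × 0.548 = 0.027 with a cytokine change of 0.3 SD, and 0.05 × 0.934 = 0.047 with 0.5 SD.

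**Step 5. Between-arm comparator.** The shared change cancels in EG minus CG. A single between-arm test on change stays at 0.05 at every d. The same joint rule on between-arm tests stays at 0.0025 (independent) or 0.009 (correlation 0.5).

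**The case against.** **A between-group test is planned.** This is true, and the design is randomised and placebo-controlled. The objection reduces the defect to a missing link: the SAP paragraph is generic, names no outcome, and leaves open whether it uses change or end values. An analyst could follow the documents and still decide hypothesis 3 on EG alone.

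**The cytokine hypothesis may be mechanistic.** If it says only that SNS moves when cytokines move, change from any cause could bear on it, and the planned correlation analyses would suit it. The rates above would then not be error rates. This cannot be excluded, because the hypothesis is not defined. The restriction to EG and the stated objective both point to an aspirin effect.

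**The sentence may mean change in EG but not in CG.** Hypotheses 1 and 2 refer to both groups, so the contrast is plausible, but it is not written. Nor is it a test of the difference between arms. With no aspirin effect, one outcome meets it with probability p(1 − p): 0.284 × 0.716 = 0.203 for n = 50 at d = 0.2, and 0.222 for n = 60. Jointly, the answer depends on the definition:

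- If each outcome must be significant in EG and not in CG, the rate is 4/5% at 0.2 SD and 6/5% at 0.3 SD (independent), and 8/9% and 11/10% at correlation 0.5. At correlation −0.5 it is lower, below 3%. In the independent case it cannot exceed 0.25² = 6.25%.
- If the joint rule must be met in EG but not in CG, it is 7/10% and 21/24% (independent), and 12/15% and 24/25% at correlation 0.5.

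**SNS may be stable.** No text predicts SNS change without aspirin, and baseline SNS is taken after acute signs settle. This stands in full: if SNS is stable, the harm does not arise. But the rule is then valid only under an assumption the plan never states, while a control arm that removes the need for it is available.

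**Conclusion.** The point holds: the rule is wrong as written and should be fixed. The first sentence of hypothesis 3 draws a conclusion from within-arm change, and nothing in the SAP links it to the control arm. The trial does not lack a between-group test; it lacks a statement that such a test decides this hypothesis.

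The missing link is certain from the text. The size of the harm is conditional. It needs both SNS and cytokines to change without aspirin, by more than roughly 0.11 to 0.22 SD depending on sample size and correlation. The high rates in the table need shared changes of 0.3 SD or more in both outcomes, and the documents neither support nor rule that out. The one-cytokine assumption also matters: the plan names only the Th1, Th2 and Th17 classes and does not say what counts as a changed profile, so counting change in any one of several cytokines would make that half easier to meet.

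The second sentence of hypothesis 3, which reads non-significance as evidence of a trait, is a separate matter and is not covered here.

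**What to change.** - Reword the first sentence of hypothesis 3 so that it rests on the EG-minus-CG difference in SNS and in the cytokine measures.
- State in the SAP which test decides it: either the listed independent-samples t or Mann-Whitney test applied to change scores, or a comparison of visit 3 values adjusted for baseline.
- Label the paired t and Wilcoxon tests within an arm as descriptive for this hypothesis.
- Say in one sentence what the cytokine hypothesis claims.
- As a secondary step, choose the cytokine measures before unblinding and give a rule for handling more than one.
- Do not substitute significance in EG with non-significance in CG; its error rate still moves with the shared change.

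**Cost.** One hypothesis and one SAP paragraph are reworded, and cytokine measures are chosen before unblinding. No new data are needed. The criterion becomes harder to meet. Differences detectable with 80% power, in SD of change, for 50 / 60 per arm:

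| Criterion | Between arms | Within EG (paired) |
|---|---|---|
| SNS alone | 0.57 / 0.52 | 0.40 / 0.37 |
| SNS and one cytokine, equal effect, independent | 0.65 / 0.59 | 0.46 / 0.42 |
| The same, correlation 0.5 | 0.63 / 0.58 | 0.45 / 0.41 |

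### Hypothesis 3 reads two significant changes within the aspirin arm as support for a cytokine mechanism, without a control contrast or a patient-level link, and gives no reading for SNS change without cytokine change

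*Combined protocol and SAP*

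**What the plan says.** Under Objective and hypotheses, the third working hypothesis gives two readings.

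- Support for the mechanism: "In case of significant change of SNS and cytokine profile in the experimental group the results would support the cytokine hypothesis".
- The contrasting outcome: "If there were no significant changes in the SNS in the experimental group, the results would support the SNS as a trait of schizophrenia".

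Hypothesis 2, just before it, expects "Changes in the cytokine profile in both patient groups", with no statement that the change should be larger under aspirin. Both arms receive antipsychotic treatment; aspirin is the addition in one of them ("Experimental group - EG: antipsychotic + Aspirin").

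The Statistical analysis plan section offers a paired test for change over time ("For the analysis of significant continuous variables over time, the Paired Samples t Test will be used if the data follow a normal distribution", otherwise Wilcoxon), an independent-samples test between arms, and one general sentence on association: "For the analysis of the dependence between two continuous variables, the value of Pearson's or Spirman's correlation coefficient will be interpreted". Strong correlations are also to be shown with a regression equation and a scatterplot. None of these analyses is tied to hypothesis 3, and no SNS–cytokine pair is named. What would count as a significant change of the cytokine profile is not defined.

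**The concern.** The rule draws a causal, mechanistic conclusion from two mean changes. Three things are missing.

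1. **A control contrast.** Change within EG mixes any aspirin effect with antipsychotic response, recovery and time. Hypothesis 2 itself expects cytokines to move in both arms.
2. **A patient-level link.** Even if both changes are shown against control, that establishes only that aspirin moved each mean. It does not show that the two movements are connected.
3. **A reading for SNS change without cytokine change.** This is the pattern that fits a cytokine route least well, and the plan is silent on it.

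At stake is the only mechanistic conclusion that the trial states in advance. The treatment comparisons themselves are not affected.

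**Working it through.** The documents give no effect size, SD or power, so there is no figure of theirs to reproduce. The calculation shows how often the rule is met when SNS change and cytokine change are unrelated between patients.

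**Inputs from the documents.** Background: the trial "would include the total of 100 to 120 patients". Statistical analysis plan: "The results will be considered statistically significant if the p value is less than 0.05".

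**Assumptions.** 1:1 allocation (50 or 60 per arm), no drop-out, two-sided tests, normal data, one SNS and one cytokine measure, the same standardised change *d* in both, and zero patient-level correlation.

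**Formulas.** Power of one test comes from the noncentral t distribution.
- Within EG (paired): noncentrality d√n, df n − 1. Example: 0.5 × √50 = 3.54, power 0.934.
- Between arms: noncentrality d√(n/2), df 2n − 2. Example: 0.6 × √25 = 3.00, power 0.844.
- Both outcomes significant when they are unlinked: the square of the single-test power.

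| Rule | d | n = 50: one test → both | n = 60: one test → both |
|---|---|---|---|
| Within EG | 0.3 | 0.548 → 0.300 | 0.628 → 0.394 |
| Within EG | 0.5 | 0.934 → 0.872 | 0.968 → 0.937 |
| Between arms | 0.3 | 0.318 → 0.101 | 0.371 → 0.137 |
| Between arms | 0.5 | 0.697 → 0.486 | 0.775 → 0.601 |
| Between arms | 0.6 | 0.844 → 0.712 | 0.903 → 0.816 |

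**Aspirin does nothing, and both arms change by 0.5 SD.** The within-EG rule is still met in 87–94% of trials. Requiring both between-arm tests to be significant brings this to 0.05 × 0.05 = 0.25% (0.26% and 0.19% in 20,000 simulated trials at n = 50 and 60).

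**Adding a patient-level link.** With no true link, a correlation test at 0.05 passes 1 time in 20, so 0.872 × 0.05 = 0.044 and 0.937 × 0.05 = 0.047. Simulation gave 4.4% and 4.5%.

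**Power for the link.** Power ≈ Φ(atanh(r) × √(N − 4) − 1.96), adjusting for arm.
- r = 0.15, N = 100: 0.151 × 9.80 − 1.96 = −0.48, power 32%. N = 120: 37%.
- r = 0.20, N = 100: 0.203 × 9.80 − 1.96 = 0.03, power 51%. N = 120: 59%.
- For 80% power, r = tanh(2.80/√(N − 4)): 0.28 at N = 100 and 0.25 at N = 120.

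Adjusting also for baseline SNS (N − 5) lowers these powers by less than half a percentage point.

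**Outcome patterns in EG as the plan reads them.**

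| SNS | Cytokines | Stated reading |
|---|---|---|
| changed | changed | supports the cytokine hypothesis |
| not changed | either | supports SNS as a trait |
| changed | not changed | none |

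**The case against.** **The contrasting outcome is stated.** A reader might infer that no result could go against the hypothesis. The documents do not support that: the sentence after the rule gives a null SNS result to the rival trait reading, so the hypothesis can fail to gain support. What stands is the narrower gap in the last row of the table.

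**The SAP plans correlations and a regression equation.** It does, and an SNS–cytokine correlation could be among them. But the paragraph names no variables and sets no criterion for hypothesis 3, so a null correlation would leave the stated verdict unchanged.

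**The phrase about the experimental group may mean relative to control.** It may, but the text does not say so. A between-arm test would remove the first gap and leave the second.

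**The percentages are chosen.** This is fair. They are squared power at assumed effects and vary widely with them. Where the two effects are real, they show how readily the rule is met; they are not error rates.

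**An association is weak evidence too.** This also stands. Cytokine change arises after randomisation and is measured with assay error. Shared recovery can create a slope with no aspirin mechanism, and true mediation can show only a weak one. This limits what a positive finding may be called, but does not rescue a rule that asks for no link at all.

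**Conclusion.** The rule as written is faulty, and this is more than missing detail: followed exactly, it returns support for changes caused by antipsychotic treatment or recovery, and for two unrelated aspirin effects. How often this would happen depends on effect sizes that the documents do not give, hence the range in the table. The logical gap does not depend on them: the rule is met at the rate at which two changes are detected, linked or not.

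Two stronger conclusions should not be drawn. First, a reader might infer that the trial cannot address the question. In fact, under Clinical Trial Design, SNS and serum are each collected at the start and at six weeks on the same numbered patients, so the weakness lies in the stated inference. Second, a reader might take a non-significant cytokine effect alongside an SNS effect as evidence against the hypothesis. Without a bound on what counts as negligible, it means only that the hypothesis is not supported.

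The point merits an amendment, but it concerns interpretation of a working hypothesis and leaves the treatment comparisons as they are.

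**What to change.** Amend hypothesis 3 and the SAP as follows.

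1. Name in advance one cytokine summary. If instead any single analyte at p < 0.05 counted as a profile change, the chance of at least one false positive would be 14%, 23% or 40% for 3, 5 or 10 independent analytes (assumed counts; 1 − 0.95^k).
2. Call the results 'consistent with' the cytokine hypothesis only if (a) SNS and that summary each differ between EG and CG, and (b) change in SNS is associated with change in the summary. Test (b) in a regression of week-6 SNS on baseline SNS, arm and cytokine change, and report the slope with its 95% CI.
3. If both outcomes change without this association, conclude only that both changed.
4. If SNS changes without a cytokine effect, state that the cytokine hypothesis is not supported. Report the CIs, and do not treat non-significance as evidence against it.
5. State the limits: the association is not randomised; two samples cannot show time order; and baseline serum (visit 1) and baseline SNS (visit 2) are taken some days apart.

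**Cost.** One regression on data already planned, and reworded conclusions. The mechanistic claim becomes harder to reach, and power is limited for weak associations: 32–59% for a partial r of 0.15 to 0.20 at N = 100 to 120, and lower with drop-out.
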